## **7.6. Examination of Subgroups**

All subgroup analyses are exploratory in nature and serve the purpose of numerical assessment of consistency of treatment effects across subgroups.

Subgroups of interest have been defined post-database lock. These are

- Age of 2 years to <12 years old
- Wound age >30 days
- Total Body Wound Burden (TBWB)  $\geq 5\%$  at Baseline
- Age of 2 years to <12 years old plus TBWB  $\geq 5\%$  at Baseline
- Age of 2 years to <12 years old at baseline plus RDEB.

In general, subgroup analyses are performed only for the 6 "subgroups of interest" (ie, 2 to < 12, target wound age >30 days, TBWB  $\geq 5\%$ , and the 2 combined groups as specified above with exception of demographics and some efficacy analyses. Details are provided in the appendices.

Subgroups for subject's age are defined based on the subject's age at Baseline. For the purpose of subgroup analysis, race will be classified as White and Non-White.

For subgroup analysis of the two primary and key secondary endpoints, -treatment effects, nominal p-values and nominal 95% CI by category of the classification variables listed above will be presented.

Based on the medical review of ARANZ SilhouetteStar system data prior to unblinding, the location of target wound will be determined to be in the flexure (eg. elbow, knee) or non-flexure region. Proportion of patients experiencing complete closure of their target wound within each visit, as well as itching and pain assessment at Day 7 are to be performed for these subgroups.

Subgroup analyses for gender, race, and region were performed for AEs and SAEs leading to d/c.

## **8. STATISTICAL ANALYSIS**

### **8.1. Disposition of Patients**

The number and percentage of patients who were screened, randomized, treated, completed, discontinued, and the primary reason for discontinuation based on the CRF (Case Report Form) termination page will be displayed. In addition, the number and percentage of subjects in each study population (ie., Intent-to-Treat population [ITT], Safety population [SAF] and Per Protocol population [PP]) as defined in Section 8.4 will be summarized by treatment group.

Same summaries will be produced for each investigational site, by country, and by region.

### **8.2. Demographic and Other Baseline Characteristics**

Descriptive summaries of demographic and Baseline characteristics will be presented for the ITT and SAF populations. If the ITT and the SAF populations are identical, then the summaries will be based on ITT population only.

Continuous variables such as patient age, weight, height/length, body mass index (BMI), body surface area (BSA) calculated by Mosseler formula, body surface area index BSAI (for lesion and wound burden), age of target wound, target wound size, and temperature will be summarized as described previously.

Categorical variables such as patient gender, race, and age (0 to 27 days, 28 days to < 2 years, 2 years to < 12 years, 12 years to < 18 years, ≥ 18 years), age of target wound (≤ Median, > Median; and 0 ≤ 30 days, 31 ≤ 60 days, 61 ≤ 90 days, > 90 days), will be summarized using number of observations and percentages for each category.

Demographics is also presented for subgroups of interest.

Medical history, including disease history and EB type, will be summarized and listed.

Age will be defined as follows:

- If age was collected instead of the birth date then, the collected value will be used,
- If the birth date was collected, then

Age = (date of informed consent date - date of birth + 1) / 365.25 and truncated to completed years.

Weight will be displayed in kg, height/length will be displayed in centimeters (cm), and temperature will be displayed in degrees Celsius (°C).

### **8.3. Protocol Deviations**

Number and percentage of subjects with major protocol deviations will be summarized for each treatment group in the ITT population and for subgroups as outlined in detail in the appendices. A listing of subjects with major protocol deviations will also be provided; major protocol deviations are further described in Section 8.4.3.

#### **8.4. Analysis Populations**

ITT population will be used for all efficacy analyses. SAF population will be used for all safety analyses. PP population will be used for supportive analyses of the efficacy endpoints.

If the SAF and ITT populations are identical, then the efficacy and safety analyses will be performed using the ITT population only.

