12.2. Study Populations

Analysis Populations

The Intent-to-Treat (ITT) population will be used for all efficacy analyses. The Safety population (SAF) will be used for all safety analyses. The Per Protocol (PP) population will be used for supportive analyses of the efficacy endpoints.

If the SAF and ITT populations are identical, then the safety analyses will be performed using the ITT population only.

Intent-to-Treat (ITT) Population

The intent-to-treat (ITT) population will be defined as all patients who have been randomized to study treatment. These patients will be analyzed according to the assigned treatment.

Safety (SAF) Population

The Safety (SAF) population is defined as all randomized patients who applied/were administered the study medication at least once. These patients will be analyzed according to the treatment actually received.

Per Protocol (PP) Population

The per protocol (PP) population will be defined as the ITT patients who have no major protocol deviations and have target wound data at baseline and from ≥ 1 post-baseline assessment.

Major protocol deviations include but are not limited to:

1. Entry criterion deviations that impact primary endpoint analyses

2. Non-compliance to study drug (as defined by compliance to study drug <70% as per patient diary)
3. Administrative dispensing errors

A final list of major protocol deviation criteria and patients who have any major protocol deviations will be documented before final database lock. A listing will also be created.

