##### **8.4.1. Intent-to-Treat (ITT) Population**

ITT population will be defined as all patients who have been randomized. These patients will be analyzed according to the assigned treatment.

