##### **8.4.2. Safety (SAF) Population**

SAF population is defined as all randomized patients who applied/were administered the study drug at least once. These patients will be analyzed according to the treatment actually received.

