##### **8.4.3. Per Protocol (PP) Population**

PP population will be defined as the ITT patients who have no major protocol deviations and have target wound data at Baseline and from  $\geq 1$  post-Baseline assessment.

Major protocol deviations include but are not limited to:

1. Entry criterion deviations that impact primary endpoint analyses
2. Non-compliance to study drug (as defined by compliance to study drug  $< 70\%$  as perpatient diary)
3. Administrative dispensing errors

A final list of patients who have any major protocol deviations will be documented before final database lock. A listing will also be created.

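### When the Safety and ITT populations coincide, safety moves to as-assigned grouping, with no condition that every patient received the assigned cream

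*SAP*

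**What the plan says.** The SAP gives each population a membership rule and, in a separate sentence, a grouping rule.

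- **ITT (SAP 8.4.1).** Membership: "ITT population will be defined as all patients who have been randomized". Grouping: "These patients will be analyzed according to the assigned treatment".
- **Safety (SAP 8.4.2).** Membership: "SAF population is defined as all randomized patients who applied/were administered the study drug at least once". Grouping: "These patients will be analyzed according to the treatment actually received".

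SAP 8.4 first sets the default, "SAF population will be used for all safety analyses", and then adds the exception: "If the SAF and ITT populations are identical, then the efficacy and safety analyses will be performed using the ITT population only". Protocol 12.2 has the exception for safety alone: "If the SAF and ITT populations are identical, then the safety analyses will be performed using the ITT population only". The main efficacy analyses are on ITT in any case, so only the safety half of the SAP sentence matters here.

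Both documents expect that study drug may sometimes be handed out wrongly. SAP 8.4.3 and Protocol 12.2 list "Administrative dispensing errors" among the major protocol deviations.

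**The concern.** As-received and as-assigned grouping give different safety tables only if some patient received a cream other than the one assigned. That is the case the grouping rule in SAP 8.4.2 exists to handle. The exception in 8.4 can override that rule in the same case, because its condition is that the populations are identical and nothing is said about treatment received.

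A patient given the other arm's cream belongs to both populations, so the error does not stop the two sets from matching. Which arm carries that patient's adverse events would then depend on an unrelated fact: whether some other randomized patient was never dosed. At stake is the correct attribution of adverse events, with a possible slight dilution of any true safety difference. Efficacy grouping is unaffected.

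**Working it through.** The plan gives no figure on this point, so there is none to reproduce. The check applies the definitions to each possible case and then illustrates the size.

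**Step 1. Apply the rules.**

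| All randomized patients dosed? | All received only the assigned cream? | Safety analysed on | Grouping that results |
|---|---|---|---|
| No | Yes | Safety | As received, same as assigned |
| No | No | Safety | As received |
| Yes | Yes | ITT | As assigned, same as received |
| Yes | No | ITT, if identical refers to membership | As assigned, differs from received |

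Only the last row is a problem. There the text yields a result that contradicts SAP 8.4.2.

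**Step 2. Can full dosing occur?** SAP 4.1 and Protocol 9.4 and 10.1 place the first application at the clinic visit, so few randomized patients should go undosed. SAP 6.2.1 nevertheless provides for patients whose first application was not at that visit, so full dosing is not guaranteed. Let q be the chance that a randomized patient is never dosed (assumed; the documents give no value), and let patients be independent. With 150 patients, the chance that all are dosed is (1 − q)^150:

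- q = 0.1%: 0.999^150 = 86%
- q = 0.5%: 0.995^150 = 47%
- q = 1%: 0.99^150 = 22%
- q = 2%: 0.98^150 = 5%

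**Step 3. Size, if the last row applies.** Inputs: 75 patients per arm (SAP 4.4); assumed true adverse event rates of 20% on one cream and 10% on the other; k patients in each arm who used the other arm's cream throughout. As assigned, the expected rates are

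- first arm: [(75 − k) × 0.20 + k × 0.10] / 75
- second arm: [(75 − k) × 0.10 + k × 0.20] / 75

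so the true difference of 10.0 points is multiplied by 1 − 2k/75.

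| k per arm | First arm | Second arm | Difference (points) |
|---|---|---|---|
| 0 | 20.0% | 10.0% | 10.0 |
| 1 | 14.9/75 = 19.87% | 7.6/75 = 10.13% | 9.7 |
| 2 | 14.8/75 = 19.73% | 7.7/75 = 10.27% | 9.5 |
| 4 | 14.6/75 = 19.47% | 7.9/75 = 10.53% | 8.9 |

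**Step 4. Does the output list settle the rule?** SAP 11.3 labels nearly all adverse event, vital sign, physical examination and skin infection tables as Safety Population. It lists demographics for ITT only, although SAP 8.2 calls for both populations unless they are identical. If the sets coincide, the demographics follow the rule but the safety labels do not. If they differ, the safety labels follow the rule but a Safety version of the demographics is missing. The list therefore does not show which grouping governs the safety tables.

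**The case against.** The strongest reply is that identical can be read to include the grouping sentence. On that reading, a Safety population with one patient in a different arm is not identical to ITT, the exception never applies in the problem case, and the clause only avoids duplicate tables. This may well be what the sponsor meant. It is not written in either document, and membership and grouping stand in separate sentences, so the reply argues for a clarification and does not remove the need for one.

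The safety labels in SAP 11.3 also count against any inference that safety was in fact moved to ITT. That stands: the documents do not show that any table was produced under the wrong grouping.

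Two stronger readings are tempting and unsupported. A reader might infer that the two populations are almost certain to coincide because the first dose is given in clinic. SAP 6.2.1 allows for exceptions, and a single undosed patient leaves the as-received rule in force. A reader might also estimate the number of affected patients from the three dispensing visits in Protocol 11 (150 × 3 = 450 dispensings) and some error rate. The documents give no rate, and not every dispensing error delivers the other arm's cream. Moreover, 300 of the 450 fall at Visits 3 and 4, where an error would leave a patient exposed to both creams, a case for which SAP 8.4.2 gives no grouping rule.

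Finally, safety is in general summarized descriptively (SAP 7.1), and major deviations and adverse events are listed by patient (SAP 8.3 and 8.7.3), so a misallocated patient could be traced. This limits the consequence but does not correct the rule.

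**Conclusion.** The point holds as a gap in a stated rule. Read literally, SAP 8.4 and Protocol 12.2 override as-received safety grouping when all randomized patients are dosed and at least one received the other cream.

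The consequence is minor. Under the assumed rates of 20% and 10%, one patient misplaced in each arm for the whole study reduces the difference from 10.0 to about 9.7 points, and four in each arm reduce it to 8.9. These figures are illustrations that rest on assumed rates and whole-study misallocation. The documents do not establish that the exception applied, that any patient received the wrong cream, or how many might have. No formal safety test and no primary efficacy result depends on it.

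**What to change.** Change SAP 8.4 and Protocol 12.2 in one of two ways: state that safety is always grouped by treatment actually received, whichever population label is used; or define identical as the same patients, each having received only the assigned cream.

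Two additions are needed for the rule to be complete. SAP 8.4.2 should say how a patient exposed to both creams is grouped, because as-received grouping alone does not place that patient. SAP 8.2 and the labels in SAP 11.3 should use the same definition, so that demographics and safety tables follow one rule.

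The cost is a few clauses, with no new data and no new type of analysis. Because Amendment 1 postdates database lock, the report should also state whether any patient received a cream other than the one assigned. If none did, the two groupings give the same tables and the point is closed.

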##### **8.4.1. Intent-to-Treat (ITT) Population**

ITT population will be defined as all patients who have been randomized. These patients will be analyzed according to the assigned treatment.

##### **8.4.2. Safety (SAF) Population**

SAF population is defined as all randomized patients who applied/were administered the study drug at least once. These patients will be analyzed according to the treatment actually received.

##### **8.4.3. Per Protocol (PP) Population**

PP population will be defined as the ITT patients who have no major protocol deviations and have target wound data at Baseline and from  $\geq 1$  post-Baseline assessment.

Major protocol deviations include but are not limited to:

1. Entry criterion deviations that impact primary endpoint analyses
2. Non-compliance to study drug (as defined by compliance to study drug  $< 70\%$  as perpatient diary)
3. Administrative dispensing errors

A final list of patients who have any major protocol deviations will be documented before final database lock. A listing will also be created.

#### **8.5. Prior and Concomitant Therapy**

The World Health Organization (WHO) Drug Dictionary Version of March 2017 will be used to classify medications. Any medication taken before and continuing after randomization, or initiated after randomization, is considered a concomitant medication. Any medication given before randomization but discontinued prior to randomization is considered a prior medication. A medication can be considered both prior and concomitant. Medications missing both start and stop dates, or having a start date prior to the last dose of study drug and missing the stop date, or having a stop date after the start of study drug and missing the start date, will be considered concomitant. Medications will also be considered concomitant if partial start and stop dates are present but it cannot be determined if the medication ended prior to start of study drug.

A summary table will be provided for each of the following in the safety population:

1. Number and percentage of subjects who had previous therapies/medications by Anatomical Therapeutic Chemical (ATC) code text and WHO drug name
2. Number and percentage of subjects who had concomitant therapies/medications by ATC text and WHO drug name

The summary of use will also be provided for the groups of drug classes of concomitant medications listed in the table below:

**Table 2: Concomitant Medications of Interest**

SD-101-6%	Placebo	Timepoint or duration	Drug Class
All subjects Subgroups of interest	All subjects Subgroups of interest	Entire study	A06A: drugs for constipation A11: vitamins A12: mineral supplements
All subjects Subgroups of interest	All subjects Subgroups of interest	Entire study	B03: antianemic drugs B05: blood substitutes and perfusion solutions J01: antibacterial drugs J02: antimycotic drugs
All subjects Subgroups of interest	All subjects Subgroups of interest	Entire study	N02: analgesic drugs N05: psycholeptic drugs N06: psychoanaleptics
All subjects Subgroups of interest	All subjects Subgroups of interest	Entire study	R06: antihistamines for systemic use
All subjects Subgroups of interest	All subjects Subgroups of interest	Entire study	V20: surgical dressings D09: medicated dressings D08: antiseptics and disinfectant drugs D06: antibiotics for derm use D03: treatment of wounds and ulcers
All subjects Subgroups of interest	All subjects Subgroups of interest	At Baseline	D07: topical dermatological corticosteroids H02: corticosteroid systemic L04A: immunosuppressant drugs

## 8.6. Analysis of Efficacy Endpoints

Table 3 in Section 8.6.2 summarizes the efficacy endpoints analyses.

### 8.6.1. Analysis of the Two Primary Efficacy Endpoints

#### 8.6.1.1. Statistical Methods

The two primary efficacy endpoints for this study are time to complete target wound closure within 3 months and the proportion of patients experiencing complete closure of their target wound within 3 months. These variables will be compared between SD-101-6% and Placebo, and tested via a step-down procedure beginning with the time to complete target wound closure.

Each endpoint might have analysis performed by primary and supportive methods.

The statistical methodology is as follows:

- Time to complete target wound closure

As clarified in the NTF, time to event analyses will be summarized using a Kaplan-Meier approach, where the event is complete target wound closure measured from the date of the first administration of the study drug to the date of wound closure. Patients will be censored if they did not have a response within 3 months, or withdraw early, before the confirmation of their target wound closing. Comparison of the treatment groups will be performed using the Cox-proportional model with Baseline target wound size, target wound age, and EB type as covariates. The p-value, hazard ratio (HR), and 95% CI (Confidence Interval) of the hazard ratio (HR) from the Cox model will be presented.

Only patients who have the Week 2 wound closure data will be analyzed.

In addition, a sensitivity analysis will be performed using the log-rank test for the comparison of the two treatment groups.

The proportional hazards assumption will be assessed by adding the treatment by time interaction into the Cox-proportional hazards model. If that interaction term approaches or reaches statistical significance, and if the Kaplan-Meier (K-M) survival curves indicate substantially varying treatment differences in cumulative proportion of patients with total wound closure, then the cumulative proportions may be compared between treatments for appropriate time periods suggested by the K-M plot. These between-treatment comparisons per time period would be via logistic regression or exact binomial tests.

The consistency of the treatment effect across each of the subgroups (see Section 7.6) will be evaluated using descriptive statistics.

As decided post-database lock, same analysis using K-M approach and Cox-proportional hazards model will be performed assuming 45 day cutoff for target wound closure. It means that any time to wound closure that is 44 days or more is going to be right censored.

- Proportion of patients experiencing complete closure of their target wound within 3 months

Complete closure of the target wound will be determined at each visit. A patient will be considered a “responder” if they experience complete wound closure at the Week 2, Months 1, 2, or 3 visits.

The proportions of “responders” (patients experiencing complete target wound closure within 3 months) in the two treatment groups will be compared using the following hypothesis testing where the null and alternate hypotheses are as follows:

$$H_0: P_0 = P_6 \quad H_a: P_0 < P_6,$$

where  $P_0$  is the proportion of patients receiving Placebo experiencing the second primary endpoint and  $P_6$  is the proportion of patients receiving SD-101-6% experiencing the second primary endpoint.

The proportion of “responders” (proportion of patients exhibiting complete closure of their target wound within 3 months of randomization) will be analyzed using the

logistic regression model with Baseline target wound size, target wound age, and EB type as covariates. The first analysis will be performed using the ITT population based on the Multiple Imputation methodology (MI) as the first imputation method for missing values, see Section 7.3.

In the case that complete separation and quasi-complete separation occurs from the logistic regression model as specified above, the explanatory variable causing the situation will be identified and excluded from the model. If the treatment factor is that variable, then the treatment effect will be tested using the chi-square test.

The p-value for the treatment comparison, odds ratio of response between the two treatment groups, and the 95% CI of the odds ratio will be presented from the logistic regression model. In addition, the unadjusted response rates for each group, the difference of unadjusted response rates between the two treatment groups, and the 95% CI of the difference using the Miettinen-Nurminen method will also be provided.

The consistency of the treatment effect across each of the subgroups (see Section 7.6) will be evaluated using descriptive statistics.

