visit and at least 60% of patients treated with SD-101-6.0 will experience complete closure of their target wound by this time (hazard ratio approximately 2.127, assuming exponential hazards over time). Note that ALL wounds are open at baseline; hence, the survival endpoint is an open wound. It is expected that fewer wounds will stay open on test treatment than on placebo; hence, the expected proportions of open wounds at 3 months are 65% on placebo and 40% on test treatment, which corresponds to a HR=2.127. These yield the 35% expected wound closures for placebo (35% = 100% - 65% surviving open), and 60% for SD-101-6.0 (60% = 100% - 40% surviving open). Using these assumptions and a 1-sided overall alpha of 0.025, approximately 150 patients will be required (75 in each group) to provide at least 86% power for time to complete target wound closure. There is estimated 85% power for the proportion of patients with complete target wound closure.

Therefore, approximately 150 patients are to be enrolled.

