**Table 3: Analysis Strategy for Efficacy Endpoints (Continued)**

Endpoint	Primary vs. Supportive Approach	Statistical Method	Analysis Population	Missing Data Approach
Change in BSAI of lesional skin at Week 2, Month 1 and Month 2, compared to Baseline	P	MMRM	ITT	MI
	S	MMRM	ITT	As observed
	S	ANCOVA	ITT	MI As observed
	S	ANCOVA on transformed data	ITT	MI As observed
	S	Descriptive Statistics	ITT	As observed
Presence of scarring of healed target wound at the visit where the complete closure is documented	P	Descriptive Statistics	ITT with wound closure	As observed
Change in target wound characteristics (ie. milia, inflammation, blistering, granulation tissue, erythema, exudate) at Week 2, Months 1, 2, and 3, compared to Baseline	P	Logistic regression	ITT	As observed
	S	Descriptive Statistics	ITT	As observed
Change in Itching and Pain at Days 1 to 6, Week 2, and Months 1, 2 and, 3, compared to Baseline	P	Logistic Regression	ITT	As observed
	S	Logistic Regression	ITT	As observed (excluding missing)
	S	Descriptive Statistics	ITT	As observed
Target Wound Closure within Week 2, compared to Baseline	P	Logistic Regression	ITT	MI
	S	Descriptive Statistics	ITT	As observed

Abbreviations: MMRM=Mixed model for repeated measures with treatment, visit, and visit-treatment interaction as fixed effects; P=Primary approach; S=Supportive approach

The analysis of key secondary efficacy variables will be as follows:

- Proportion of patients experiencing complete target wound closure at Month 2  
 This assessment will be analyzed using the same approach as the second primary endpoint.
- Proportion of patients experiencing complete target wound closure at Month 1

This assessment will be analyzed using the same approach as the second primary endpoint.

- Change in lesional skin based on BSAI at Month 3 compared to Baseline

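### The separation rule removes the whole EB-type factor from the confirmatory logistic models on the strength of the outcomes, and leaves pooling undefined if only some imputed datasets separate

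*SAP*

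**What the plan says.** SAP 8.6.1.1 analyses the second primary endpoint by logistic regression, adjusting for baseline target wound size, target wound age and EB type. If complete or quasi-complete separation occurs, "the explanatory variable causing the situation will be identified and excluded from the model". If treatment is the variable at fault, "then the treatment effect will be tested using the chi-square test".

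SAP 8.6.2 carries this into the key secondary endpoints. For closure at Month 2 and at Month 1 it says: "This assessment will be analyzed using the same approach as the second primary endpoint". Day 7 itch and Day 7 pain use the same method, with the baseline score and EB type as the only covariates. SAP 7.5 places all of these in the step-down sequence, where a failure ends formal testing of everything below it.

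SAP 7.3 plans five imputed datasets for the closure endpoints. MIANALYZE is to combine them into one treatment coefficient, confidence interval and p-value. SAP Table 3 and Section 8.6.2 show that itch and pain are not multiply imputed; a missing score counts as non-improvement.

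Neither document mentions penalised or exact logistic regression or the collapsing of EB types, and neither gives expected numbers per EB type. Neither says what happens if separation appears in only some imputed datasets.

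**The concern.** EB type enters as one factor with three types (Simplex, Recessive Dystrophic, Junctional non-Herlitz). Separation in one small type therefore removes adjustment for all three, although the contrast between the two larger types remains estimable. Three things follow.

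- Whether a pre-specified prognostic covariate stays in a confirmatory model is decided by the outcomes. Its removal also changes which odds ratio is being estimated.
- For the closure endpoints, imputed values can break the separation in some of the five datasets and not in others. The SAP does not say whether EB type then leaves all five models or only some. Coefficients from different covariate sets do not estimate the same quantity and should not be pooled.
- The chi-square fallback yields no coefficient for MIANALYZE, and no other pooling rule is given.

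At stake are the estimate and some power for the second primary endpoint and for the key secondary endpoints that use this model.

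**Working it through.** **1. The plan's own figures.** Protocol 12.1 states that "the expected proportions of open wounds at 3 months are 65% on placebo and 40% on test treatment", "which corresponds to a HR=2.127". Check: ln 0.40 / ln 0.65 = 2.127.

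On the second primary endpoint it states: "There is estimated 85% power for the proportion of patients with complete target wound closure". With 75 per group, closure of 35% and 60%, and one-sided 0.025:
- log OR = ln(0.60/0.40) − ln(0.35/0.65) = 1.0245
- SE = √(1/45 + 1/30 + 1/26.25 + 1/48.75) = 0.338
- power = Φ(1.0245/0.338 − 1.96) = 85.8%; one-sided Fisher exact gives 85.4%

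For the first primary endpoint, 75 × 0.35 + 75 × 0.60 = 71.25 expected events. Freedman's formula, Φ(√71.25 × 1.127/3.127 − 1.96), gives 86.0%, in line with the stated 86%. These figures reproduce and are not in dispute.

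**2. How often the rule would fire.** Under the plan's exponential assumption, closure by month t is 1 − 0.65^(t/3) on placebo and 1 − 0.40^(t/3) on active. The average of the two arms is p = 19.8% at Month 1 (13.4% and 26.3%), 35.3% at Month 2 and 47.5% at Month 3. The chance that all m patients of a type share one outcome is p^m + (1 − p)^m. The values of m are assumptions.

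| m | Month 1 | Month 2 | Month 3 |
|---|---|---|---|
| 5 | 33% | 12% | 6.4% |
| 8 | 17% | 3.1% | 0.8% |
| 10 | 11% | 1.3% | 0.2% |
| 15 | 3.6% | 0.1% | under 0.1% |

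This takes the small type to close at the average rate. If it heals worse, the rule fires more often (step 3). The documents give no improvement rates for itch or pain, so no such figure can be computed for them.

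**3. What it costs once it fires.** The simulation used N = 150, placebo closure near 35% in Recessive Dystrophic patients (intercept −0.62), true adjusted log OR 1.10, effects of −0.4 and −0.3 per SD for wound size and wound age, and 1,000 separated datasets per row. All EB-type numbers and effects are assumptions. Columns b show the log odds of closure relative to Recessive Dystrophic.

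| Junctional n, b | Simplex n, b | Share separated | Power: drop / Firth | Mean log OR: drop / Firth |
|---|---|---|---|---|
| 3, 0 | 20, +0.5 | 25% | 89.3% / 88.2% | 1.12 / 1.09 |
| 5, 0 | 20, +0.5 | 6.5% | 88.6% / 88.4% | 1.12 / 1.09 |
| 5, −1.5 | 20, +1.0 | 33% | 87.4% / 88.2% | 1.08 / 1.10 |
| 10, −2.5 | 20, +1.0 | 39% | 85.5% / 86.7% | 1.03 / 1.09 |
| 10, −2.5 | 30, +1.5 | 39% | 81.3% / 84.5% | 0.99 / 1.11 |

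In the last row the log OR falls by (1.10 − 0.99)/1.10 = 10%. With no treatment effect, one-sided rejection was 2.2–2.9% after dropping and 2.3–3.1% with Firth (nominal 2.5%, Monte Carlo SE about 0.5 point).

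Simulation at the Month 1 level (true log OR 0.95, one type of 8 or 12 patients) gave 0.81–0.90 after dropping and 0.93–0.95 with Firth, with power 0–4 points lower after dropping. Further runs with a strongly prognostic EB type put the loss at about 2–6 points. With a non-prognostic EB type, dropping cost nothing and could gain 2–3 points.

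**4. Averaged over trials.** Share separated times loss in the last three rows: 0.33 × 0.8 = 0.3, 0.39 × 1.2 = 0.5 and 0.39 × 3.2 = 1.2 points of power.

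**The case against.** The rule is explicit and pre-specified, and it keeps type I error near nominal, so one may call Firth a preference. On error control that stands. A reader might infer that a data-dependent model inflates false positives; neither the documents nor the simulation support this.

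A reader might also infer that the rule always biases the odds ratio toward 1. It does not: with a weakly prognostic EB type the log OR after dropping was 1.12 against a true 1.10. Part of the movement seen elsewhere is non-collapsibility, since a model without a prognostic covariate targets a different odds ratio and its test stays valid.

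Other limits also stand:
- A sparse type does not trigger the rule by itself; all its patients must share one outcome.
- The trigger would be more frequent at Week 2 and in subgroup tables, but SAP 7.5 and 7.6 make those exploratory.
- SAP 7.3 carries an observed closure forward without imputation. Datasets can therefore disagree only if a small type has uniform observed outcomes and also has missing patients.
- The chi-square branch is practically unreachable in the full sample: no placebo closure by Month 1 among 75 patients has probability 0.65^25, about 0.00002.

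What the objection does not answer is that SAP 7.3 promises one pooled coefficient, while 8.6.1.1 allows the five datasets to have different models.

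**Conclusion.** The point holds as a limited one: it should be changed, but it does not threaten the trial. The rule makes the covariate set of confirmatory logistic models depend on the outcomes, and it leaves pooling undefined for the multiply imputed closure endpoints. At the plan's rates it matters mainly at Month 1, is small at Month 2, and is negligible at Month 3 once a type has about 10 patients. A small type that heals much worse than the others would raise those chances.

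Given separation, a strongly prognostic EB type means a log OR roughly 10% nearer zero and a few points of power lost; a non-prognostic one means no loss. These sizes rest on assumed EB-type numbers and effects, because the documents give neither.

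A reader might take this to put the study's success criterion in doubt. It does not: SAP 6.3.1 and 7.5 rest success on the first primary endpoint alone, and that Cox analysis is outside the rule.

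**What to change.** Replace both fallback sentences in SAP 8.6.1.1 with one rule. If separation occurs, whichever variable causes it, fit Firth penalised-likelihood logistic regression with the full pre-specified covariate set.

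- **Closure endpoints:** if any of the five imputed datasets separates, use Firth in all five and pool the treatment coefficients and standard errors by Rubin's rules.
- **Day 7 itch and pain:** use a profile penalised-likelihood test and confidence interval, since nothing is imputed.

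The imputation model in SAP 7.3 is itself a logistic regression that includes EB type, so the same paragraph should say how separation is handled there.

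The cost is a paragraph and one model option. The downside is slight shrinkage of the odds ratio and possibly 1–3 points of power if EB type is not prognostic. SAP Section 2 says that this amendment already contains changes made after database lock. If this change is also made after lock, label it as such and report the result under the existing rule beside it.
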